11.1.1 Rationale for the Assumed Conversion Rate of 10% in the Control Arm

The primary outcome of the D2d trial is “time to confirmed diabetes”. The diagnosis of diabetes is based on ADA-based cutoffs for FPG, 2hPG and HbA1c, as defined in section 9. The incidence rate of diabetes can vary considerably based upon a number of factors. In prior type 2 diabetes prevention trials, conducted in a variety of populations worldwide,^{5,6,11-14,17,265-269} the diabetes incidence rates (based only on FPG/2hPG criteria) varied from 2.4% to 23% per year. The most relevant data for the proposed D2d trial come from the DPP (U.S.)⁵ and DREAM (21 countries)¹² studies. The DPP trial recruited participants with FPG 95-125 mg/dL, 2hPG 140-199 mg/dL, and BMI \geq 24 kg/m². The DPP placebo group had a cumulative incidence of diabetes of ~29% during the 2.8-year mean follow-up (approximately 10% per year). The DREAM trial started recruitment with impaired fasting glucose and impaired glucose tolerance (defined as FPG 110-125 mg/dL and 2hPG <200 mg/dL) or impaired glucose tolerance (defined as FPG \leq 125 mg/mL and 2hPG 140-199 mg/dL) but later expanded the criteria to include isolated impaired fasting glucose (defined as FPG 110-125 mg/dL and 2hPG <140 mg/dL). The DREAM study had a cumulative incidence of diabetes in the placebo arm of 25% over a 3-year mean follow-up (estimated ~8-9% annually). In two other large type 2 diabetes prevention trials with alpha-glucosidase inhibitors, the cumulative incidence rates in the placebo arm were 42% over 3.3 years (reported 12.1% annually; STOP-IT/Europe)¹¹ and 36% over 2.8 years (estimated ~12-13% annually; Voglibose trial/Japan).¹³ In the CANOE trial (Canada), the cumulative incidence rates in the placebo arm were 42% over 3.9 years (estimated ~10% annually).²⁶⁹ Importantly, in nearly all these studies, the observed annual incidence rate was higher than that assumed in the pre-trial sample size calculations (6.5% [predicted] vs. 11% [actual] in DPP; 4.5% vs. ~8-9% in DREAM; 7% vs. 12 in STOP-IT; 7.7% vs. 12-13% in the Voglibose trial).

We expect the diabetes incidence rate in the D2d study to be at the high end of the rate that would be predicted from the mean annual incidence rate (~9-11%) reported in previous diabetes prevention studies because: (1) the study is targeting a population similar to the DPP (U.S. adults at high risk for type 2 diabetes with similar BMI and age at entry); (2) the definition of ‘at risk for diabetes’ requires 2-out-of-3 glycemic criteria, which will identify participants at higher risk for progression to diabetes; (3) the study will use the current ADA glycemia criteria for diagnosis of diabetes (addition of HbA1c), which will likely raise the incidence rate of diabetes compared with the above studies.

In relation to point (3) above, only one of the published studies on prevention of type 2 diabetes included HbA1c as a criterion for both inclusion and outcome assessment.¹³ The study reported a conversion rate to diabetes in the placebo arm of 36% over 2.8 years. However, this study was conducted in Japan and its definitions of pre-diabetes or diabetes were not consistent with the current ADA criteria; therefore, its relevance to the D2d study is not clear. Adding HbA1c alters the epidemiology of pre-diabetes and diabetes and makes it difficult to predict incidence rates. We reviewed relevant data from recent cross-sectional observational studies that have evaluated the impact of adding HbA1c as a diagnostic criterion. As expected, there is considerable overlap between the HbA1c and FPG/2hPG criteria. Overall, the addition of HbA1c appears to increase prevalence of both pre-diabetes and diabetes.²⁷⁰⁻²⁷⁵ For example, Lu et al identified 37% more individuals as having

pre-diabetes by HbA1c 5.6-6.5% and identified 9% more individuals as having diabetes by HbA1c >7%.²⁷⁵ Data from NHANES show that an additional ~6% of participants are identified as having diabetes when HbA1c >6.5% criterion is used in addition to FPG/2hrPG.^{271,273} In a recent systematic review that examined ranges of HbA1c and progression to diabetes, the A1c range of 6.0 to 6.5% was associated with a 25 to 50% incidence of diabetes over 5 years.²⁷⁶ In the CaDDM trial,²⁴ among 202 fully screened participants with available data on FPG/2hPG/HbA1c, the addition of HbA1c≥6.5% increased the prevalence of newly diagnosed diabetes from 2% to 7% (unpublished data provided by [name]). Finally, in the Pima Indian Longitudinal Study (unpublished data provided by [name]), after excluding participants with diabetes at baseline (based on clinical and the 2010 ADA glycemic criteria), there were 392 participants with pre-diabetes (by 2010 ADA criteria) with mean age of 42 years, BMI 39 kg/m² and HbA1c 5.7%. The cumulative incidence of diabetes during a 5-year follow-up period increased from 36% using the old criteria, to 39% using the new expanded criteria, which represents an increase of 12% in the annual incidence rate if HbA1c is added to the FPG/2hPG criteria.

[figure not shown]
In summary, based on available data in the literature and results of unpublished analyses shown above, it is expected that the addition of HbA1c to the FPG/2hPG diagnostic criteria will increase the number of cases of diabetes diagnosed during follow-up compared to the FPG/2HPG criteria alone. Furthermore, the definition of the main inclusion criterion, pre-diabetes, requiring 2 of 3 criteria (identifying participants at relatively high risk) will increase the incidence rate compared to previous studies. However, the planning committee elected to be conservative in its estimate to ensure adequate power for the primary outcome and has assumed an incidence rate of 10% per year (hazard rate = 0.1054) in sample size calculations.

11.1.2 Rationale for the Assumed Hazard Ratio of 0.75

The planning committee relied on published observational *longitudinal* data and short-term intervention studies to estimate a plausible hazard ratio.

Observational studies: In the Nurses' Health Study, the highest 25OHD concentration (>33 ng/mL) was associated with a reduction in incident diabetes by ~50% over ~10-year follow-up period.¹⁸ In the Framingham Offspring Study, participants in the highest tertile of predicted 25OHD score (>22 ng/mL) had a 40% lower incidence of diabetes during a 7-year follow-up period.²¹ These results are consistent with other recently published observational data.^{26-28,195,196} In a recent meta-analysis that combined data from all available longitudinal observational studies, the pooled relative risk of t2DM comparing the highest with the lowest quartile of 25OHD was 0.59 (0.52, 0.67), with little heterogeneity between the 11 studies included (3,612 cases and 55,713 non-cases) (Figure 11.1).¹⁹⁶

Figure 11.1. Meta-analysis (Forouhi et al) of the association between blood 25OHD concentration and incident type 2 diabetes.¹⁹⁶

In another meta-analysis by Song et al, the pooled relative risk for incident type 2 diabetes was 0.62 (95% confidence interval [CI]:0.54-0.70) for the highest vs. lowest 25OHD concentration (Figure 11.2).¹³⁸ A linear trend meta-regression analysis showed that each 4 ng/mL increment in 25OHD level was related to a 4% lower risk of diabetes (RR, 0.96; 95% CI, 0.94-0.98; *p* for linear trend<0.0001; Figure 11.3).¹³⁸

Based on the observational data, if the proposed D2d intervention (4,000 IU/day of vitamin D) increases participants' mean 25OHD to approximately 40-45 ng/mL from ~20 ng/mL,^{197,200-202} then risk reduction will be approximately 20-25%.

Figure 11.2. Meta-analysis (Song et al) of the association between blood 25OHD concentration and incident type 2 diabetes.¹³⁸

[figure not shown]
[figure not shown]

Figure 11.3. Relation between blood 25OHD concentration and risk of incident type 2 diabetes, modeled by quadratic spline regression.¹³⁸

There are two observational studies of particular importance and relevance to the D2d study that were not included in the above meta-analyses: In the DPP study, among participants with pre-diabetes, there was an inverse linear association between 25OHD and incident diabetes, after multivariate adjustment including change in BMI and physical activity, with the hazard ratio for incident diabetes being lowest (0.46; 95%CI, 0.23 to 0.90) in the highest category (25OHD \geq 50 ng/mL) compared to the lowest category (25OHD $<$ 12 ng/mL) with no evidence of a threshold.²⁵ In another observational study, progression from pre-diabetes to type 2 diabetes was reduced by 73% among those with 25OHD $>$ 28 ng/mL compared to those with 25OHD $<$ 18 ng/mL.¹⁹⁵

Intervention studies: In the CaDDM trial, 2,000 IU/day of vitamin D₃ supplementation, which raised 25OHD to 31 ng/mL, improved measures of beta cell function (disposition index) by ~40% and glycemia (HbA1c) by ~50% after 4 months.²⁴

After taking into consideration all published data and short-term mechanistic studies on vitamin D and diabetes, a hazard ratio of 0.75 (i.e. 25% reduction in risk in the intervention arm) was used as the assumed treatment effect in sample size calculations. A reduction of this magnitude would clearly be clinically significant to public health.

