2.4 Potential impact on human health

The “excitement” surrounding the role of vitamin D for diabetes, and other chronic diseases, has led to dramatic increases in 25OHD assays done as part of routine medical care and in supplementation with very high doses of vitamin D to “improve” vitamin D status. Medicare payments for vitamin D testing nearly quadrupled between a 2-year span, 2006 and 2008, to \$129 million. A decade ago, these payments were only about \$1 million. Concurrently, spending on vitamin D supplements has increased tenfold in the last 8 years to \$425 million in 2009, which represents a growth of 81% from 2008.¹⁵⁹ Manufacturers of vitamin D assays and supplements have rushed to claim a piece of the “vitamin pie;” however, such enthusiasm is premature as the evidence is extrapolated from observational studies, which are severely limited, as outlined above. Furthermore, simply raising 25OHD level does not always translate to favorable outcomes.^{150,160}

The need for such a trial has been recognized in the recent literature in editorials, reviews and book chapters.^{32,46,47,148,161-184} Of importance, the 2011 Institute of Medicine report on dietary reference intakes (DRI) for calcium and vitamin D recognized as a major limitation in setting the DRI the lack of long-term trials with vitamin D supplementation, and *identified diabetes as one of the most promising non-skeletal areas that require further research with rigorously done trials to confirm the promising results seen in observational and mechanistic studies.*¹⁸⁵ The Endocrine Society guidelines also note that “trials that evaluate the effects of vitamin D doses in the range of 2,000 to 5,000 IU/day on non-calcemic health outcomes are desperately needed.”¹⁷⁶

The proposed trial, therefore, addresses an important and timely question and has the potential for significant impact in the clinically important areas of vitamin D and type 2 diabetes prevention with extensive public health implications especially given that the cost of supplementation with vitamin D is inexpensive compared to treating the chronic disease and its complications. We expect the D2d study results to define the role of vitamin D supplementation in modifying type 2 diabetes risk. If the trial

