Based on published observational and short-term mechanistic intervention studies,^{18-22,27,28,34,45,47,194} it appears that a plasma 25OHD concentration of approximately 30-50 ng/mL is required to detect a protective effect of vitamin D in relation to type 2 diabetes, if present. In an observational study in the Nurses' Health Study, the median 25OHD in the highest quartile, which was associated with an approximate 50% risk reduction in incident type 2 diabetes, was 33 ng/mL.²² This level was consistent with another observational study by Knekt et al (mean 25OHD in the highest quartile, 30 ng/mL).^{27,28} Of particular relevance to the D2d trial, in a longitudinal observational study in the Diabetes Prevention Program (DPP) cohort, participants with pre-diabetes with baseline plasma 25OHD \geq 30 ng/mL had a 28% risk reduction in incident diabetes over a 3-year period, after adjustment for the DPP lifestyle intervention, while participants with 25OHD concentration \geq 50 ng/mL had a 56% risk reduction.²⁵ In the Stockholm Diabetes Prevention Program, progression from pre-diabetes to type 2 diabetes was reduced by 62% among those with 25OHD $>$ 28 ng/mL compared to those with 25OHD $<$ 18 ng/mL.¹⁹⁵ In a recent meta-analysis, the pooled relative risk of type 2 diabetes comparing the highest with the lowest quartile of 25OHD was 0.59 (0.52, 0.67), with little heterogeneity between the 11 studies included (3,612 cases and 55,713 non-cases).¹⁹⁶ In another meta-analysis,¹³⁸ 9 publications were identified that provided data from 13 independent cohorts involving 65,721 participants and 3,567 incident cases of diabetes.^{22,25,28,37,39,42-44,137} Comparing the highest to the lowest category of 25OHD levels, the pooled relative risk for incident diabetes was 0.65 (95% CI, 0.55-0.77). A linear trend meta-regression analysis showed that each 4 ng/mL increment in 25OHD levels was related to a 4% lower risk. In the CaDDM trial, among participants with pre-diabetes (which is the target population in the D2d study), daily supplementation with 2,000 IU of vitamin D₃ achieved a mean 25OHD concentration of 31 ng/mL in the active arm, which was associated with improvements in beta cell function (disposition index) by approximately 40% and glycemia (HbA1c) by approximately 50% after 4 months.²⁴ In a six-month trial by von Hurst et al, insulin resistance with vitamin D supplementation improved the most when end-of-study 25OHD concentration was higher than 32 ng/mL.³⁴ Although one can extrapolate these data to recommend a much higher target 25OHD concentration, there is very limited longitudinal observational data²⁵ and no intervention studies to support targeting much higher levels.

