4.3.5 Duration of Intervention and Follow-up Period

It is anticipated that participants who are randomized early will be followed for approximately 4 years for development of the primary outcome, diabetes. Because D2d is an event-driven trial, follow up periods are estimates and will depend on rates of enrollment and retention. There are no definitive data to determine the optimum duration of exposure to vitamin D required to affect diabetes risk. In an observational study in the Nurses' Health Study, women with the highest 25OHD concentration at baseline had a reduction in diabetes by 40% over an approximate 10-year follow-up period.²² In the Framingham Offspring Study, participants in the highest tertile of predicted 25OHD score had a 40% lower incidence of diabetes during a 6-year follow-up period.²¹ Of particular relevance to the D2d trial, in the Diabetes Prevention Program (DPP) cohort, participants with pre-diabetes who had a plasma 25OHD concentration ≥ 30 ng/mL at baseline had a 28% risk reduction in incident diabetes over a 3-year period, after adjustment for the DPP lifestyle intervention.²⁵ In the Stockholm Diabetes Prevention Program, among participants with pre-diabetes, the risk of progression to type 2 diabetes was reduced by 62% among those with blood 25OHD above 28 ng/mL compared to those with 25OHD lower than 18 ng/mL over a 8-year follow-up, which corresponds to a 23% reduction for each 4 ng/mL increase in blood 25OHD concentration.¹⁹⁵ These results are consistent with other observational cohorts.²⁶⁻²⁸ A post-hoc analysis of a completed trial showed a reduction of approximately 90% in FPG and insulin resistance (HOMA-IR) in participants with pre-diabetes after 3 years of supplementation with vitamin D.¹⁹ In the RECORD trial, a trend towards reduced diabetes risk was seen with vitamin D supplementation after 2-4 years of follow up.¹⁴⁸ In the CaDDM trial, among participants with pre-diabetes, 2,000 IU/day of vitamin D₃ improved measures of beta cell function (disposition index) by approximately 40% and glycemia (HbA1c) by approximately 50% after 4 months.²⁴ In addition to vitamin D-specific mechanisms, the planning committee also took into consideration additional issues, including practical ones, when deciding on the follow-up period, as follows: (1) a shorter follow-up period will minimize "study fatigue" by study personnel and participants, and will maximize retention; (2) a shorter follow-up period will allow the study to be

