11. SAMPLE SIZE CALCULATIONS AND DATA ANALYSIS

11.1 Sample Size Calculation (Power Analysis)

The primary aim of D2d is to assess whether, in participants at risk for diabetes, oral daily vitamin D₃ supplementation will reduce the rate of progression to incident diabetes when compared to placebo.

The D2d study is designed as an event-driven trial to assure that the intended power to detect the hypothesized treatment effect (hazard ratio = 0.75, see below) is achieved irrespective of the event rate in the placebo arm.

The following considerations were used to determine the required number of events:

- 1) The primary study outcome is “time to confirmed diabetes”.
- 2) The primary hypothesis will be tested at a two-sided type 1 error rate (alpha) of 0.05.
- 3) If vitamin D therapy is superior to placebo, the hazard ratio will be 0.75 in the vitamin D arm as compared to the placebo arm.
- 4) The study is designed to have power of 90% to detect a hazard ratio of 0.75.

Based on these assumptions, the required number of events is 508²⁶⁴. To achieve the intended power, D2d will continue until 508 primary events have occurred.

Based on the following assumptions, it is estimated that the required (i.e. randomized) sample size will be 2,382 participants.

- 5) Participants will be recruited over a 2-year period (“accrual period”)
- 6) The expected study duration will be approximately 4 years plus an end-of-study visit over a period not to exceed three months.
- 7) The incidence rate of confirmed diabetes will be 10% per year (hazard rate = 0.1054) in the placebo group.
- 8) The loss-to-follow-up (i.e. going “off study”) rate will be up to 5% per year of follow-up (hazard rate = .0513).
- 9) If vitamin D therapy is superior to placebo, the hazard ratio will be 0.75 in the vitamin D arm as compared to the placebo group.

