Kaplan-Meier estimates of “time to confirmed diabetes” distributions will be calculated for each treatment group. The log-rank test will then be used to perform an unadjusted comparison of the time-to-event distributions in the two treatment groups. Follow-up of participants who withdraw or are lost to follow up will be “censored” on the date of their last follow-up visit. All p values examined for statistical significance will be two tailed, and p-values below 0.05 will be considered statistically significant. Cox proportional hazard models²⁷⁸ will be used to calculate an estimate of the adjusted hazard ratio. To construct the model for the adjusted analysis, we will first construct a regression model that does not include the indicator for treatment group. Age, race, ethnicity, BMI, and other variables (fasting glucose, 2-hr glucose, HbA1c and 25OHD) to be specified a priori will be forced into the model. Variables will then be added in a step-up fashion from a list of candidates selected a priori. Covariates making a statistically significant contribution to the proportional hazards regression model will be included in the multivariate model. When the step-up procedure has been completed, the covariate for treatment group will be added to the model. The regression coefficient for treatment group in this multiple regression model will be the adjusted estimate of the log hazard ratio.

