4 PRIMARY ANALYSIS & SUPPORTING ANALYSES

The *primary analysis* of D2d will assess whether, in participants with pre-diabetes, oral daily vitamin D₃ supplementation reduces the rate of progression from pre-diabetes to incident diabetes (=primary outcome).

All randomized participants are included in the analysis. Kaplan-Meier estimates of “time to confirmed diabetes” distributions will be calculated for each treatment group. The log-rank test will then be used to perform an unadjusted comparison of the time-to-event distributions in the two treatment groups. Follow-up of participants who do not complete the study (e.g. withdrew) will be "censored" on the date of their last follow-up encounter (see below). Cox proportional hazard modeling will be used to compare the risk of incident diabetes in the two groups.¹ The model will include an indicator for the randomized intervention as its main predictor variable. Clinical site at randomization will be a stratifying factor. The baseline variables (BMI, race, as entered in SPIRS) used to stratify the randomization will also be included as stratifying factors.

The p-value from the primary analysis will be based on the chi-square statistic from a likelihood ratio test obtained from proportional hazards models with and without the term for intervention arm. Comparisons of the intervention groups will be performed per the ITT principle, with all randomized participants grouped per their intervention assignment at randomization, regardless of adherence. Unless otherwise specified, p values will be two tailed, and values below 0.05 are considered statistically significant.

Definitions of follow-up time and censoring. Follow-up time for the primary outcome will be censored at the date of the *last assessment for diabetes with data in the electronic data capture system as of the cutoff date (as defined in the Manual of Procedures – section 20)*.

Censoring for participants *with diabetes* occurs at the date of the diabetes event, as shown in the *Diabetes Outcome* form in EDC. Specifically,

- If the diagnosis of diabetes is made within the study (i.e., using results by the Central Laboratory), the date of onset of diabetes is defined as the date of the first diagnostic glycemc value.
- If the diagnosis of diabetes is made outside of study (i.e., adjudicated), the date of onset of diabetes is determined during the adjudication process.

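### Do the 20–25% projection, power stated at 25% only, and the conflicting literature figures in Protocol 11.1.2 call for a change to the plan?

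*Protocol*

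**What the plan says.** Protocol 11.1 fixes the design effect and the target: "The study is designed to have power of 90% to detect a hazard ratio of 0.75", at two-sided alpha 0.05, which requires 508 events. The trial continues until they have occurred.

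Protocol 11.1.2 explains the choice. One paragraph uses observational data and a rise in mean 25OHD from about 20 to 40–45 ng/mL: "then risk reduction will be approximately 20-25" per cent. The section closes by setting the hazard ratio at 0.75 in view of all the published data and the short-term mechanistic studies, and calls a reduction of that size clinically significant.

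On reporting, SAP section 4 says "The p-value from the primary analysis will be based on the chi-square statistic from a likelihood ratio test", comparing proportional hazards models with and without the treatment term. Protocol 11.2 says Cox models "will be used to calculate an estimate of the adjusted hazard ratio". Neither sentence mentions a confidence interval. Protocol 2.4 sets the ambition: "We expect the D2d study results to define the role of vitamin D supplementation in modifying type 2 diabetes risk".

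On the literature, 11.1.2 says of the Stockholm pre-diabetes cohort (reference 195) that "progression from pre-diabetes to type 2 diabetes was reduced by 73" per cent. For the same 25OHD contrast, 4.3.1.2 says "progression from pre-diabetes to type 2 diabetes was reduced by 62" per cent, and 4.3.5 also has it "reduced by 62% among those with blood 25OHD above 28 ng/mL compared to those with 25OHD lower than 18 ng/mL".

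**The concern.** The stated power covers only the favourable end of the range that 11.1.2 derives. If the true reduction were 20%, the trial would miss it more often than the 90% figure suggests. With no interval named in either document, a reader of a non-significant result might take the 90% statement to mean that the projected benefit had been excluded. Given the ambition in 2.4, that would be a serious misreading.

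The conflicting figures add to the unease. 11.1.2 is the written justification for the design effect, and where it disagrees with another section it carries the larger number. That invites the question of whether 0.75 rests on misquoted evidence.

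**Working it through.** **1. The plan's own figure.** Inputs from Protocol 11.1 and 7.3.1: hazard ratio 0.75, two-sided alpha 0.05, power 90%, allocation 1:1. Schoenfeld's formula, which the protocol cites:

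events = 4 × (1.960 + 1.2816)² / (ln 0.75)² = 507.8, rounded up to 508. The figure reproduces.

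**2. Power across the range.** Power = Φ(|ln HR| × √(508/4) − 1.960), with √127 = 11.27.

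| True HR | Calculation | Power |
|---|---|---|
| 0.72 | Φ(0.3285 × 11.27 − 1.960) | 96% |
| 0.75 | Φ(0.2877 × 11.27 − 1.960) | 90% |
| 0.80 | Φ(0.2231 × 11.27 − 1.960) | 71% |

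The 0.72 row corresponds to the 28% reduction that 4.3.1.2 cites from the Diabetes Prevention Program cohort at 25OHD of 30 ng/mL or more. For scale, 90% power at 0.80 would take 845 events (844.1 rounded up). Simulating the single look at 70% of events (Z of 3.09, then 1.96 at the end) gives 90.1% at 0.75 and 71.1% at 0.80, so the interim analysis does not alter the picture.

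**3. What an interval would show.** The standard error of the log hazard ratio is about 2/√508 = 0.0887, so the 95% limits are the estimate divided and multiplied by exp(1.960 × 0.0887) = 1.190.

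- Significance needs an observed hazard ratio below 1/1.190 = 0.840.
- The lower limit reaches 0.75 at an estimate of 0.892 and 0.80 at 0.952.
- A non-significant estimate from 0.840 to 0.952 therefore leaves 0.80 inside the interval. From 0.840 to 0.892 it leaves 0.75 inside as well.
- If the true value is 0.80, 29% of trials are non-significant. Subtracting the 2.5% whose lower limit lies above 0.80 leaves about 26% that are non-significant with 0.80 still in the interval.

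**4. Can the interval be had from what is planned?** The likelihood ratio test requires fitting the Cox model with the treatment term, and that fit gives the log hazard ratio and its standard error. Even from a published estimate and p-value alone it can be recovered approximately. An estimate of 0.90 has z = 0.1054/0.0887 = 1.19, and the interval is 0.90/1.190 to 0.90 × 1.190, or 0.76 to 1.07.

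**5. Where 20–25% comes from.** 11.1.2 gives a 4% lower risk per 4 ng/mL. A rise of 20 to 25 ng/mL is 5 to 6.25 steps, and 4% × 5 to 4% × 6.25 is 20% to 25%. The same slope appears in 2.3 and 4.3.1.2. None of the disputed study results is an input.

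**6. The figures side by side.**

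| Item | 11.1.2 | Elsewhere |
|---|---|---|
| Stockholm cohort (ref. 195), >28 vs <18 ng/mL | 73% | 62% (4.3.1.2, 4.3.5) |
| Meta-analysis (ref. 138), highest vs lowest | RR 0.62 (0.54–0.70) | RR 0.65 (0.55–0.77) (2.3, 4.3.1.2) |
| Nurses' Health Study | about 50% (citing ref. 18) | about 50% (4.3.1.2) and 40% (4.3.5), both citing ref. 22 |
| Expected mean 25OHD, from about 20 ng/mL | 40–45 | 35–40 (4.3.1.2) |

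The first two rows are plain mismatches. In the third, 11.1.2 agrees with 4.3.1.2, and 4.3.5 is the outlier. The citation in 11.1.2 looks misplaced, because the reference list titles reference 18 as an intake study and reference 22 as the plasma 25OHD study. The fourth row is not one cited result. It is two forward projections with overlapping but different citations; they meet at 40, and 4.3.1.2 qualifies its range by reference to winter.

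**The case for a change.** The strongest case for acting is the last row of that table, because the 25OHD range does feed the projection. Taking 35–40 ng/mL from 4.3.1.2 with the same slope, the rise is 15 to 20 ng/mL and the reduction 15% to 20%, where power at 508 events is 45% to 71%. Compounding the slope as 0.96 per step gives 14% to 18.5% and power of 41% to 63%. On that reading even 20% is optimistic, and setting out in advance how a null result will be read would be a sensible safeguard at the cost of a sentence or two.

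The arithmetic stands, but the inference to a change does not. The projection is conditional and rests on one observational slope. The design effect is justified on wider grounds, including stronger data in people with pre-diabetes and clinical importance, and the concern does not dispute 0.75. Writing 0.75 and 0.80 into the SAP as reading bounds would also fix thresholds on a 25OHD range that the documents leave unsettled. Under 35–40 ng/mL, 0.80 would no longer be the lower end.

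It is also true that the SAP names a p-value where it could name an estimate with its interval, and that the estimate in Protocol 11.2 comes from a covariate-adjusted model rather than the SAP's stratified one. That is missing detail about routine output. Kaplan-Meier curves by arm and a hazard ratio are planned, and nothing suggests that the interval would be withheld.

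**Conclusion.** No change to the plan follows. The 508 events and the 90% power at a hazard ratio of 0.75 are correct as stated, and a 25% reduction lies inside the 20–25% projection, so the two statements do not contradict each other. Quoting power at the design effect alone is normal practice. The 71% at 0.80 is useful background but corrects no stated number.

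The unstated confidence interval is a gap that any analyst fills: it comes with the specified Cox model and would be about the estimate divided and multiplied by 1.19. A reader who sees it will see what a non-significant result leaves open.

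The conflicting study results are clerical. The contrasts they describe, from 35% (RR 0.65) to 73%, are all larger than the 25% used for design, whichever member of each pair is right, and none enters the event calculation. The documents alone cannot show which values are right, so anyone quoting them later should go back to the sources. The two 25OHD ranges are projections that touch at 40 ng/mL. They bear on how optimistic 0.75 is, but not on the event count or the test.

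These numbers assume proportional hazards, 1:1 allocation, a standard error of 2/√508 for the log hazard ratio and a final analysis at 508 events. The interim look makes no material difference.
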